17. Currently participating in an investigational drug or another device trial (excluding registries);
18. Evidence of an acute myocardial infarction ≤30 days before the index procedure;
19. Need for emergency surgery for any reason;
20. True porcelain aorta (i.e. Heart Team agrees the aorta is not clampable for SAVR);
21. Extensive mediastinal radiation;
22. Liver failure (Child-C);
23. Reduced ventricular function with left ventricular ejection fraction (LVEF) <20% as measured by resting echocardiogram;
24. Uncontrolled atrial fibrillation (eg. resting heart rate >120bpm);
25. Pregnancy or intent to become pregnant prior to completion of all protocol follow-up requirements;
26. End stage renal disease requiring chronic dialysis or creatinine clearance < 20 cc/min;
27. Pulmonary Hypertension (systolic pressure> 80mmHg);
28. Severe Chronic Obstructive Pulmonary Disease (COPD) demonstrated by Forced Expiratory Volume (FEV1) < 750cc;
29. Frailty assessments identify:
  - Subject is < 80 years of age and three or more of the following apply
  - Subject is ≥ 80 years of age and two or more of the following apply
    - Wheelchair bound
    - Resides in an institutional care facility (eg. nursing home, skilled care center)
    - Body Mass Index < 20 kg/m^2
    - Grip strength <16 kg
    - Katz Index score ≤ 4

- o Albumin < 3.5 g/dL;
- 30. Marfan syndrome or other known connective tissue disease that would necessitate aortic root replacement/intervention.

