### C.4.5 Enrollment and Randomization

Prior to randomization and enrollment of a subject, the following must occur:

- Confirm patient signed informed consent
- Confirm patient meets all of the inclusion and none of the exclusion criteria, including approval by the Heart Team

Subjects will be considered enrolled into the trial at the time of randomization (i.e. time of treatment assignment). Randomization will occur only if the patient meets all inclusion criteria and does not meet any exclusion criteria and has been assessed by the Heart Team as being an appropriate candidate for randomization in the SURTAVI trial.

Due to the inclusion/exclusion criteria, not all patients that consent to the trial will be enrolled. All sites will be required to maintain a record of patients screened for the trial meeting general inclusion criteria who have signed the approved informed consent document. For subjects that do not meet trial criteria, the reason for not continuing in the trial must be documented and recorded in the EDC system. Patients consented but not randomized will be considered screen failures and no further trial-related follow-up will be required.

Subjects must have their TAVI or SAVR procedure no later than 30 days post-randomization.

Trial randomization will not be blinded. Once randomization is complete and a treatment arm is assigned, crossover from SAVR to TAVI treatment is not permitted. The sponsor will strictly monitor device dispensation to ensure that only those subjects randomized to the TAVI treatment arm receive the Medtronic CoreValve™ or CoreValve™ Evolut™ R TAV.

Distribution of the subjects within the trial groups will be controlled at the implanting sites by means of central randomization using interactive voice/web randomization service (IXRS). The randomization scheme will be securely stored at the IXRS provider.

---

 Based on protocol design, the time of enrollment will be the same as randomization which is a deviation from ISO 14155 (2011).

Randomization with an assignment to the treatment arm or control arm (TAVI or SAVR) will be executed in a 1:1 ratio. Stratified randomization by investigational site and by the need for coronary revascularization will be used to ensure subjects will be allocated to each comparison group proportionately. Additionally, a blocked randomization scheme with random block sizes will be used within each stratum.

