#### C.4.8 Assessments done at discharge (both SAVR and TAVI)

Prior to hospital discharge (or within 7 days post-index procedure, whichever occurs first) the following tests and procedures must be performed and data collected:

- Physical Examination
  - Vital signs
  - Major system findings
  - Skin Assessment – refer to Radiation Exposure and Data Collection, **Appendix R.23**
- Concomitant Medications
  - Use of relevant medications (diuretics, aspirin, anticoagulants, ACE-I, ARB, beta-blockers, statins and anti-platelets)
- Routine Laboratory Tests:
  - Complete Blood Count:
    - White Blood Count
    - Hematocrit
    - Hemoglobin
    - Platelet Count
  - Creatinine and Creatinine Clearance
  - Cardiac Enzymes (CK/CK-MB)
  - International Normalized Ratio (INR), if applicable
  - Activated Partial Thromboplastin Time (aPTT)
  - B-type Natriuretic Peptide (BNP) or NT-proBNP
  - Liver Panel:
    - ALT
    - AST
    - Albumin
  - Sodium
  - Potassium
- Neurological Assessments
  - National Institute of Health Stroke Scale (NIHSS)
  - Modified Rankin Score (mRS)
  - Mini-Mental State Exam (MMSE-2:SV)
  - Additional Neurological testing:
    - Visual Fields Testing
    - Gait Assessment
    - Hand Function
    - Writing Evaluation
    - Drawing Assessment
- Transthoracic Echocardiogram (TTE)
  - Comprehensive transthoracic 2D echocardiogram (TTE) should be performed at least 24hours post-procedure but prior to discharge to assess device success (and no later than 7 days, whichever comes first)
  - Echocardiograms will be performed according to Echocardiography Procedures found in **Appendix R.7**
- 12-lead Electrocardiogram
- Adverse Event review

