### *C.5.2 Reporting*

Investigators are required to keep records on “all relevant observations, including records concerning adverse device effects (whether anticipated or unanticipated)” [21 CFR 812.140; ISO 14155 (2011)]. Adverse event collection will begin from the point of trial enrollment to trial closure. All new or worsening (from baseline) adverse events and technical observations will be captured on the AE eCRF through the 24-month follow-up visit. It is the responsibility of the Investigator to assess the subject for adverse events and capture the required adverse event information on the AE eCRF.

Once a subject has completed their 24-month scheduled follow-up visit only serious adverse events, major adverse events, cardiovascular events, device-related adverse events, including device related technical observations, unanticipated adverse device effects (UADE) or unanticipated serious adverse device effects (USADE), all strokes (CVAs) and deaths will be required to be reported. Reference section C.5.1 Adverse Events for event definitions and criteria. Medtronic representatives or their designees will conduct monitoring visits to review source documentation and verify the complete and accurate capturing of adverse events.

The Investigator must also notify the responsible IRB/MEC regarding new and significant safety information and any event identified by Medtronic that requires expedited FDA, and/or local regulatory agency, reporting as serious, unexpected, and related to the investigational device. It is the responsibility of the investigator to ensure site specific IRB/MEC safety reporting requirements are met.

Medtronic Clinical will ensure all device-related adverse events and all procedure-related SAEs are processed according to internal policies and procedures. When necessary, Medtronic Field Assurance will respond to sites in writing with the findings related to the product experiences.

The general procedure for investigators reporting any adverse event is as follows:

- Report the event to Medtronic as soon as possible but no later than the timeframes outlined below. (At the time of Site Initiation, sites will be provided with the telephone and other applicable contact information of the appropriate Medtronic designee).
- Complete all sections of the Adverse Event eCRF.
- Each unique event/diagnosis must be documented separately.

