The statistical approach for these analyses is Bayesian. The prior distributions for  $\pi_T$  and  $\pi_C$  in these calculations are Beta (1,1). The threshold  $\Psi$  is designated to be 0.971 for non-inferiority testing and  $\Psi_{\text{SUP}} = 0.989$  for superiority testing; these values are selected by trial-and-error to achieve a type I error (under simulation) of at most 0.05 for non-inferiority testing and at most 0.025 for superiority testing. Of note, establishing  $P(H_{\delta=0} | \text{data}) > \Psi_{\text{SUP}}$  means that superiority has been established to a standard equivalent to a nominal significance level of 0.025 (1-sided), but this does not automatically mean that a labeling claim of superiority is supported. See "Multiplicity Considerations" (Section C.12) for additional requirements regarding labeling claims on secondary objectives.

Further details of planned analyses are provided in the SAP.

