- The incidence of conduction disturbance requiring permanent pacemaker implantation will be provided at 30 days, 6 months, 12 months, 18 months, 24 months, and annually thereafter up to 5 years, separately for new onset and pre-existing conduction disturbance. The statistical method will be the Bayesian version of a comparison of proportions (with predictions).
8. Change in NYHA class from baseline at 30 days, 6 months, 12 months, 18 months, 24 months, and annually thereafter up to 5 years.
- For each subject with paired data, the number of classes changed from baseline (-3, -2, -1, 0, 1, 2, or 3) will be calculated at 30 days, 6 months, 12 months, 18 months, 24 months, and annually thereafter up to 5 years. The endpoint will be evaluated between groups using a Bayesian version of a t-test.
9. Change in distance walked during 6-minute walk test (6MWT) from baseline to 30 days, baseline to 12 months, and baseline to 24 months.

All subjects who are able to perform the six-minute walk evaluation at the time of the follow-up visit will be included in the analysis.

The endpoint will be evaluated using a Bayesian version of a t-test.

10. Ratio of days alive out of hospital versus total days alive assessed at 12 months and 24 months follow-up.

The proportion of post procedure days alive out of hospital against total days alive will be compared between groups at 12 and 24 months. The numerator will be the number of days alive out of hospital, and the denominator will be the number of post procedure days alive as of the last follow-up date. All hospitalizations will be included in this analysis, including hospitalization for device implant.

In addition, days alive out of hospital will be compared between groups at 12 months and 24 months.

The endpoint will be evaluated using a Bayesian version of a t-test.

11. Quality of Life (QoL) change from baseline at 30 days, 3 months, 6 months, 12 months, 18 months, 24 months, and annually thereafter up to 5 years.

The Kansas City Cardiomyopathy Questionnaire (KCCQ), SF-36, and EuroQoL (EQ-5D) will be assessed at baseline, 30 days, 6 months, 12 months, 18 months, 24 months, and annually thereafter up to 5 years. SF-36 and EQ-5D will also be assessed at 3 months. All subjects completing the questionnaires will be evaluated and the reasons for missing data will be provided.

The endpoint will be evaluated using a Bayesian version of a t-test .

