For each treatment group, the proportion of subjects with a neurologic injury (stroke, TIA, or encephalopathy) at discharge or at 7 days post-index procedure (whichever occurs first) will be calculated. The numerator will be the number of subjects with a neurologic injury (stroke, TIA, or encephalopathy) at discharge or at 7 days post-index procedure (whichever occurs first), and the denominator will be the number of subjects in that treatment group. Results will also be presented separately for disabling stroke, non-disabling stroke, TIA, and encephalopathy. Proportions will be compared between groups using Bayesian version of a comparison of proportions.

17. Index procedure related MAEs

Index procedure-related MAE events will be summarized and event rates will be provided at 30 days. The numerator will be the number of procedure-related MAE events experienced by the end of the 30-day follow-up visit, and the denominator will be the number of subjects evaluated at the 30-day follow-up visit (or a later follow-up) plus the number of subjects not evaluated but who experienced a procedure-related MAE event prior to the end of the follow-up visit window.

The endpoint is descriptive and no statistical hypothesis test will be performed.

18. Length of index procedure hospital stay

The length of TAVI or SAVR hospital stay will be summarized for all subjects undergoing a trial procedure.

The endpoint will be evaluated between groups using a Bayesian version of a t-test.

19. Presence of atrial fibrillation at post-procedure, discharge, 30 days, 6 months, 12 months, 18 months, 24 months, and annually thereafter up to 5 years.

The statistical method will be the Bayesian version of a comparison of proportions (with predictions).

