### ATRIAL FIBRILLATION

Atrial fibrillation will be classified according to the International Consensus on Nomenclature and Classification of Atrial Fibrillation; A Collaborative Project of the Working Group on Arrhythmias and the Working Group on Cardiac Pacing of the European Society of Cardiology and the North American Society of Pacing and Electrophysiology, Europace 2003, Vol 5.

- **Paroxysmal:** spontaneous termination within 7 days and most often <48 hours
- **Persistent:** is not self-terminating; lasts longer than 7 days; or prior cardioversion
- **Permanent (accepted):** does not terminate, or terminated but relapsed; no cardioversion attempt

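### Secondary endpoint #19 compares atrial fibrillation presence without using baseline AF status, so a difference in new AF is diluted by (1 − baseline AF share) and cannot be separated from change in pre-existing AF

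*Combined protocol and SAP*

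**What the plan says.** Endpoint #19 (protocol C.6.8.1) reads "Presence of atrial fibrillation at post-procedure, discharge, 30 days, 6 months, 12 months, 18 months, 24 months, and annually thereafter up to 5 years". The method is the Bayesian comparison of proportions with predictions. The entry names no denominator, no baseline condition and no new-onset category.

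AF at baseline is compatible with entry. Exclusion 24 (C.3.6.2) removes only "Uncontrolled atrial fibrillation (eg. resting heart rate >120bpm"). Randomization is stratified by site and need for revascularization (C.4.5, C.6.5.2), not by AF. The O.2 definition classes AF as paroxysmal, persistent or permanent, and does not separate new from pre-existing.

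Endpoint #7, pacemaker implantation for conduction disturbance, is reported "separately for new onset and pre-existing conduction disturbance".

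A 12-lead ECG is scheduled at screening, at baseline, within 48 hours after the procedure in both arms, at discharge, and at every visit that #19 lists (Table 3). The discharge assessment is due "Prior to hospital discharge (or within 7 days post-index procedure, whichever occurs first").

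AF can also reach the adverse-event data: "All new or worsening (from baseline) adverse events and technical observations will be captured on the AE eCRF through the 24-month follow-up visit" (C.5.2). After 24 months, cardiovascular events remain reportable.

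On analysis detail, C.6.5.2 says "Further details of planned analyses are provided in the SAP". The SAP text on #19 is not in the part of the combined document examined here.

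**The concern.** A reader will probably look to #19 to learn whether one procedure causes more AF than the other. Subjects already in AF at entry say nothing about new AF, but they count in the numerator and denominator of a presence comparison. A moderate difference in new AF therefore looks smaller than it is. A null result could mean no effect on new AF, or an effect too diluted to see. If the arms also differed in how pre-existing AF evolved, a single prevalence figure could not show which effect was present.

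What is at stake is the interpretation of one secondary endpoint, reported at every visit to 5 years. The primary endpoint and the claims hierarchy in C.6.10 are not touched.

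**Working it through.** **Plan figure to reproduce.** There is none. The plan gives no rate, effect size or power for #19.

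**Inputs.** From the plan: 1600 mITT subjects at 1:1, so 800 per arm (C.6.5.2); up to 6% missing at 24 months (C.6.6); about 15% mortality at 24 months (C.6.5.2). Assumed, because the plan is silent: the baseline AF share b, the new-AF rates, and AF presence q among baseline-AF subjects.

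**Identity.** In each arm, presence = b·q + (1 − b)·new. With equal b in both arms,

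difference in presence = (1 − b)·(difference in new AF) + b·(difference in q).

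If q is the same in both arms, the second term is zero and a 5-point difference in new AF becomes 4.0, 3.5 or 3.0 points at b = 20%, 30% or 40%.

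**Power.** Normal approximation, two-sided 0.05: Φ[(d − 1.96·SE0)/SE1], with SE0 pooled and SE1 unpooled. Take b = 30% and new AF 10% vs 15%.

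- New onset, 800 × 0.7 = 560 per arm: d = 0.050, SE0 = 0.01976, SE1 = 0.01971, power 72%.
- Presence, q = 100% in both arms: 0.30 + 0.07 = 0.370 vs 0.30 + 0.105 = 0.405; d = 0.035, SE0 = 0.02436, SE1 = 0.02434, power 30%.
- Presence, q = 50% in both arms: 0.15 + 0.07 = 0.220 vs 0.15 + 0.105 = 0.255; d = 0.035, SE0 = 0.02128, SE1 = 0.02126, power 38%.

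A simulation with Beta(1,1) priors and a 0.975 posterior threshold agrees: 71.6%, 29.8% and 37.7%.

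**Sensitivity**, with q equal to 100% in both arms:

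| Assumption | Presence | New onset |
|---|---|---|
| b = 20%, 10% vs 15% | 42% | 77% |
| b = 40%, 10% vs 15% | 22% | 65% |
| b = 30%, 5% vs 8% | 14% | 53% |
| b = 30%, 10% vs 20% | 81% | above 99% |
| b = 30%, 10% vs 30% | above 99% | above 99% |
| b = 30%, 10% vs 15%, 752 per arm (800 × 0.94) | 29% | 69% |
| b = 30%, 10% vs 15%, 639 per arm (800 × 0.85 × 0.94) | 25% | 62% |

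**If q differs by arm** (purely hypothetical; b = 30%, new AF 10% vs 15%). With q = 50% vs 60%, the presence difference is 3.5 + 3.0 = 6.5 points and power is 85%, above the new-onset figure. With q = 60% vs 50%, it is 3.5 − 3.0 = 0.5 points and power is 6%. The two terms can add or cancel, and the total does not show which.

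**Effect of stratifying presence by baseline AF.** The target is still the overall 3.5-point difference, but its variance now uses within-stratum terms only: 0.7² × (0.09 + 0.1275)/560 + 0.3² × 2q(1 − q)/240.

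- q = 100%: SE = 0.0138, power 72% (30% unstratified).
- q = 50%: SE = √(0.000190 + 0.000188) = 0.0194, power 44% (38% unstratified).

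So using baseline AF improves even the presence comparison.

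**The case against.** Presence is a legitimate estimand. Randomization balances b in expectation, so the comparison of prevalence is valid, and dilution exists only relative to new onset. This stands. A reader might infer that #19 is biased toward one arm, and nothing in the documents supports that.

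A reader might also infer that effects in the two groups are likely to cancel, because the AF definition describes paroxysmal AF as having "spontaneous termination within 7 days and most often <48 hours". That explains why q can be below 100%, not why it should differ by arm. C.4.7.2 bars Maze procedures, which removes one obvious arm-specific cause. The adding and cancelling cases above show what the wording cannot distinguish. They are not forecasts.

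New AF is partly captured elsewhere. Adverse-event rules record new or worsening events, C.5.2 makes a documented pre-existing condition reportable only if its nature or severity changes, and cardiovascular events stay reportable after 24 months. It would be wrong to say that new AF goes unrecorded. But #19 does not refer to these data, "Trial randomization will not be blinded", and telemetry runs until discharge, so detection time follows length of stay. Adverse-event AF is support, not a substitute for scheduled ECGs.

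Other limits also stand. Every AF rate above is an assumption. The subgroup on presence of co-morbidities (C.6.12.1) might include AF, but its list is not in the part examined. Endpoint #7 counts an event by type of disturbance, so it is an analogy rather than a direct precedent. The absence of #19 from the list in C.6.7.2 carries little weight, since #4 to #6 are absent too.

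**Conclusion.** The point holds in a limited form. As worded, #19 is a valid comparison of prevalence that ignores baseline AF. A difference in new AF enters with weight (1 − b) and cannot be separated from change in pre-existing AF. The weight is exact when b is the same in both arms among those assessed at the visit; deaths or missed visits that differ by arm would add a further term.

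On the assumed rates (b = 30%, new AF 10% vs 15%, equal q in both arms), power is 30% to 38% for unadjusted presence against 72% for new onset. The loss shrinks as the effect grows and vanishes by 10% vs 30%. These figures show scale only; #19 has no power target to miss.

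A reader might take this as a threat to the trial's conclusions. It is not: #19 is outside the testing hierarchy in C.6.10 and supports no labeling claim. This is a minor improvement in analysis and reporting, conditional on the SAP not already containing it.

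**What to change.** Add one sentence to #19 and to the SAP. Define baseline AF as AF in the medical history or on the screening or baseline ECG. Keep overall presence, stratified by baseline AF. At each listed time point also report (a) new-onset AF among subjects without baseline AF and (b) AF presence among subjects with it.

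On time points:

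- Use the ECG due within 48 hours of the procedure (C.4.7.1, C.4.7.2, Table 3) as the peri-procedural assessment, because its window is the same in both arms.
- Treat the discharge ECG as supportive. Its timing follows length of stay, and C.6.10.1 hypothesizes a shorter stay after TAVI.
- Do not restrict the main time points to 30 days and later, which would miss much short-lived peri-procedural AF.
- Use adverse-event AF as supporting evidence.

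The cost is small. The ECGs are already scheduled and medical history is already taken, though the case report forms should be checked for a specific AF field. Denominators shrink: at an assumed b of 30%, group (a) has about 560 per arm and group (b) about 240, with a 95% half-width near 9 points at 50% presence (1.96 × √(0.5/240) = 0.089). Visit ECGs will still miss short episodes between visits. If the SAP already splits by baseline AF, a cross-reference in #19 is enough.

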### C.6.8.2 Secondary Endpoints Assessed for TAVI Only

The following secondary endpoints will be assessed for the TAVI cohort subjects only:

20. Device success defined as follows:

- Absence of procedural mortality AND
- Correct positioning of a single prosthetic heart valve into the proper anatomical location AND
- Intended performance of the prosthetic heart valve (no prosthesis-patient mismatch and mean aortic valve gradient <20 mmHg or peak velocity <3 m/s, AND no moderate or severe prosthetic valve regurgitation\*)
  - Assessed acutely in a resting state, either within 24-48 hours after the index procedure or before hospital discharge

\*Refers to VARC-2 definitions

Device success, as defined above, will be calculated for all subjects undergoing the TAVI procedure.

The endpoint is descriptive and no statistical hypothesis test will be performed.

21. Procedural success, defined as device success and absence of in-hospital MACCE.

Procedural success, as defined above, will be calculated for all randomized subjects undergoing the TAVI procedure.

The endpoint is descriptive and no statistical hypothesis test will be performed.

22. Evidence of prosthetic valve dysfunction at 30 days, 6 months, 12 months, 24 months, and annually thereafter up to 5 years.

The number of subjects with evidence of prosthetic valve dysfunction will be evaluated at 30 days, 6 months, 12 months, 18 months, 24 months, and annually thereafter up to 5 years. Point estimates and 95% BCIs for each time point will be presented using methods described below in the Bayesian version of a comparison of proportions (with predictions).

23. Resheath and Recapture (combined) success rate.

The success rate will be analyzed for all subjects in whom the resheath or recapture feature is attempted. The number and percentage of successful resheath or recapture attempts combined will be calculated. Separate resheathing and recapturing success rates will also be calculated.

The endpoint is descriptive and no statistical hypothesis test will be performed.

